Advanced MRI techniques such as diffusion-weighted imaging allow for the detection of early ischemic changes in the brain. Diffusion-weighted imaging is an MRI sequence capable of demonstrating changes within minutes of experimental ischemia. It is believed that ischemia-induced energy depletion increases the influx of water from the extracellular to the intracellular space, restricting water motion and resulting in a bright signal and low calculated apparent diffusion coefficient. Although there is wide individual variability, the apparent diffusion coefficient signal remains low for 4 days, pseudonormalizes at 5–10 days, and increases thereafter. This temporal evolution of the diffusion-weighted imaging signal allows one to determine the age of a stroke and differentiate acute from chronic ischemia. Investigations combining conventional MRI with diffusion-weighted imaging have revealed new small lesions after cardiac surgery in 26%–50% of patients. In our own series, we found DWI lesions after surgery in 56% of patients. The lesions are broadly distributed in the brain and often have a watershed distribution with/without an embolic signature. Watershed strokes (i.e., lesions in end-vascular territories) in the general population are usually secondary to focal hypoperfusion, although the mechanism in cardiac surgical patients is not as certain. Most diffusion-weighted imaging lesions that are seen after cardiac surgery are not associated with clinically detected stroke, and preliminary analysis suggests that they may occur without detectable short-term cognitive decline. However, in these studies, patient follow-up might have been too short to detect a relationship between “silent” MRI cerebral infarctions and cognitive decline, or the cognitive battery might not have been sensitive to the functions of the actual injured brain regions. Regardless, new diffusion-weighted imaging lesions do represent ischemic brain injury, as they can become brain infarction when re-examined with conventional MRI 1–2 weeks later. Furthermore, in the general population, clinically “silent” infarction detected with brain imaging is increasingly recognized to be associated with cognitive decline, depression, and reduced functional capacity. Combined diffusion-weighted imaging and perfusion-weighted imaging (PWI) will enable us to determine whether lesions detected by the former method occur in relatively hypoperfused brain areas. Although diffusion-weighted imaging is sensitive for detecting ischemic brain injury, post-cardiac surgery lesions may occur in brain areas not involved with higher cognitive function. Thus, combining detection of lesions by diffusion-weighted imaging with clinical neurologic end points (including cognitive deficits) will provide a highly sensitive evaluation of perioperative brain injury. The findings will be especially important for examining mechanisms and/or prevention of brain injury related to cardiac surgery.

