### ***Patient Randomization***

Patients will be prospectively randomized after anesthesia induction, but before CPB, using a computer generated randomization program into one of two single-blinded groups:

- 1) Blood pressure intervention group (Intervention Group) in which mean arterial pressure during surgery is targeted to be kept above the patient's lower CBF autoregulatory threshold based on continuous monitoring of mean velocity index or cerebral oximetry index (**see CBF Autoregulation Measurements**) or
- 2) Control Group in which mean arterial pressure is maintained during surgery, including CPB, using institutional standard of care.

**Blinding:** Clinicians caring for the patients will participate in managing blood pressure in the Intervention Group and, thus, cannot be blinded. Individuals making the neurologic assessments and performing data analysis will be blinded to the intraoperative management group, providing effective double blinding.

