Trained delirium assessors (authorized research members) will obtain a history of current symptoms from the patient, care providers, and family; review medical records; and perform a mental status exam and cognitive screens that will include the Mini Mental State Exam (MMSE) and abbreviated digit span. This information will be used to rate the CAM, producing a binary outcome for the presence or absence of delirium in the past 24 h. The DRS-R-98, which yields a delirium severity rating, will also be completed. If a patient is unable to respond verbally to questions because of intubation and mechanical ventilation, the CAM-ICU version will be administered. This instrument has sensitivities of 76%–80% and a pooled specificity of 96% in the ICU.

**Neurocognitive Function:** A component of the endpoint of this study is cognitive decline after surgery compared with the patient's baseline. Cognitive testing will be performed within two weeks before surgery, 4–6 weeks after surgery, and 1 year after surgery. Most elective cardiac surgical procedures are performed on patients admitted to the hospital the day of surgery. Assessing baseline cognitive status in patients during an outpatient visit is confounded by time constraints and anxiety that might bias the data and affect enrollment. Nonetheless, we have extensive experience in performing cognitive testing

on the day before cardiac surgery. For patients already admitted to the hospital, cognitive testing and other preoperative assessments will be performed on the ward. For patients who will be admitted the day of surgery, testing will occur either after their preoperative visit with their surgeon or by a separate visit specifically for the purposes of the study. For outpatients, testing before surgery will be at NMH.

Postoperative cognitive testing will be performed at the patient's postoperative surgical clinic visit, in NMH which usually occurs 4–6 weeks after surgery, and again at 1 year after surgery.

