Our goal for cognitive testing is not to test hypotheses about specific types of cognitive decline or about injury to specific brain regions. We have selected neuropsychologic tests that assess a number of cognitive domains known to be affected by cardiac surgery. They have the advantage of being standardized. They are also brief and easy to administer and score; the total administration time is approximately 35–45 min. Based on our previous experience, this focused approach is highly feasible for testing surgical patients. The battery is listed in Appendix B and consists of the Rey Auditory Verbal Learning Test, a test of verbal learning and memory; Rey Complex Figure Test, an assessment of visual memory; Controlled Oral Word Association Test, a test of executive functions; Symbol Digits Modalities Test, a test of psychomotor speed and attention control; Trail Making A and B, tests of visuomotor speed, attention, and executive functions; Grooved Pegboard Test, a measurement of fine motor dexterity and speed; Beck Depression Inventory, a self-reported scale of depression symptom severity; and the State-Trait Anxiety Inventory, a measurement of anxiety symptoms. The patients are also evaluated with the SF-36 short form of the RAND Medical Outcomes Study (MOS) health-related quality of life questionnaire. This questionnaire is a multi-item scale that measures 8 health-related concepts: physical function, social function, physical role, emotional role, mental health, energy, pain, and general health perceptions. The standardized scores for each of the 8 quality-of-life domains range from 0 (worst) to 100 (best). The SF-36 has been used in previous studies to assess quality of life in cardiac patients and chronically ill populations. Cognitive decline will be defined as a decrement in performance from baseline to postoperative testing of at least 1 standard deviation (SD) in two or more tests, or 2 SD in one test. It has been shown that this definition is unlikely to classify random test-retest variability as decline but is nonetheless sensitive enough to detect actual postoperative change in cognitive performance.

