**Aim 1b: To assess whether targeting MAP to a level above an individual's lower CBF autoregulatory threshold during CPB reduces the frequency of cognitive decline 1 year after surgery compared with the use of standard blood pressure management.** In Aim 1, we will test whether the Intervention and Control groups have the same risk of the primary composite neurologic endpoint of stroke, DWI lesion, or cognitive decline 4 to 6 weeks after surgery (i.e., null hypothesis). This will be done using a two-sided test of proportions at 5% significance level. We will first calculate and report the relative risk (RR) of composite neurologic outcome by comparing the Intervention and Control groups without adjusting for any potential confounders (i.e., the unadjusted RR). In addition, we will construct an adjusted estimate of RR using a generalized linear model (GLM) with Poisson distribution and robust standard errors. The candidate models will include study group as the primary independent variable as well as extra- or intracranial arterial stenosis determined by MRA, patient age, gender, and baseline risk factors that are assumed to be highly predictive of the outcome, such as history of hypertension, diabetes, or prior stroke. To assess potential effect modification by cerebral arterial stenosis, age, gender, hypertension, diabetes, or prior stroke (Aim 1a), we will calculate the unadjusted RR stratified by these variables. We will use a test of homogeneity to compare stratum-specific estimates of RR. Finally, we will use the model developed in Aim 1 to report stratum-specific adjusted estimates of RR by introducing appropriate interaction terms of these variables and study group in the GLM model. We will compute the Z-score for the cognitive tests to normalize the distribution to the control data. The individual Z-scores will be combined into an average score and re-normalized. To assess postoperative change in cognitive function for up to 1 year (Aim 1b), we will use population-average marginal models estimated using generalized estimating equations (GEE) with exchangeable working correlation structure. The model will include assessment time with 2 indicator variables for 1 year and 4 to 6 weeks postoperation and baseline as the reference group as well as Intervention Group, and their interaction to test whether postoperative trajectory of cognitive function differs by group.

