## Statistical Analysis Plan

Tabular and graphical methods of data exploration will be used to evaluate variable distributions over the perioperative time period. When conducting modeling, we will determine the influence of the outliers on model fit. If the influence is high, we will consider excluding the outlier/s. We will explore the extent to which CBF autoregulation changes over the perioperative period. Univariate distributions for all study variables will be evaluated. We will explore potential confounders as variables strongly predictive of the outcomes (a priori and in the data) and differentially distributed between the study arms. Results of these analyses will be used to refine the analyses and guide model building and selection.

The cognitive outcome will be assessed as change from baseline in a composite cognitive Z score 4 to 6 weeks after surgery. The Z score will be calculated for individual tests at each testing time point with the mean and SD of baseline tests of all patients. Timed tests will be multiplied by '-1' so that higher scores represent better performance. Individual Z scores will be combined into an average Z-score, calculated from the average of the non-missing individual test Z-scores. These will then be renormalized using the mean and standard deviation at baseline. A difference between pre- and post-test  $> 0.3$  is considered cognitive decline.

Early stopping rules: N/A

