Although perfusion-weighted imaging provides an indication of whether a brain area is relatively hypoperfused, it cannot necessarily distinguish whether a brain infarct results from embolism and/or hypoperfusion. Small emboli in well-perfused areas might be transient, but those in areas of hypoperfusion might persist (slow “washout”). In this study, we will count the number of TCD-detected microembolic signals to adjust statistically for the number of emboli in patients with and without diffusion-weighted imaging lesions. Although this study will provide only inferential data on the mechanism of brain injury, the combination of MRI indices and our determination of duration during CPB that mean arterial pressure is below the individual’s CBF autoregulatory threshold, combined with emboli monitoring with TCD, will provide important clinical mechanistic insights.

Failure to obtain study data after a patient is discharged from the hospital (i.e., at the 4- to 6-week postoperative testing sessions) could confound analysis of the secondary cognitive end points of the trial. Multiple reasons might cause patients not to comply with follow-up testing, including death, severe stroke, and discharge to a secondary care facility. Postoperative testing is coordinated to occur during the patient’s postoperative clinic visit with his/her surgeon.

Off-pump CABG surgery is performed in <10% of patients at our institution but is not performed in patients undergoing combined CABG and valve surgery. Although performance of CABG surgery “on-” versus “off-pump” has not been shown to impact neurologic outcomes remarkably based on prospectively randomized trials, it is possible that new data may become available during this trial that might support the decision to perform more surgeries without CPB. Such a decision could conceivably influence recruitment. However, the number of procedures performed at our hospital and the number of patients projected for this study suggest that a sufficient number of patients will be recruited during the planned period of study.

Providing additional information about functional capacity including performance of instrumental ADLs, as well as about ability to drive. This carries minimal additional medical risk to the participant beyond routinely held structured preoperative interview – increased anxiety due to extension of regular pre-operative interview time.

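### Two different definitions of cognitive decline at 4 to 6 weeks, a component of the primary composite, with nothing to say which one applies

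*Combined protocol and SAP*

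**What the plan says.** The Neurocognitive Function paragraph (under Blood Pressure Management) opens with "A component of the endpoint of this study is cognitive decline after surgery". It schedules postoperative testing at 4 to 6 weeks and at 1 year. It then has decline "defined as a decrement in performance from baseline to postoperative testing of at least 1 standard deviation (SD) in two or more tests", with a 2 SD fall on one test as the alternative. This is called the per-test rule below.

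The Statistical Analysis Plan section says "The cognitive outcome will be assessed as change from baseline in a composite cognitive Z score 4 to 6 weeks after surgery". Each test is standardised to the baseline mean and SD of all patients, timed tests are reversed, the available Z scores are averaged, and the average is renormalised to baseline. It ends: "A difference between pre- and post-test $> 0.3$ is considered cognitive decline". This is called the composite Z rule below.

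Study Statistics, Aim 1, tests the "primary composite neurologic endpoint of stroke, DWI lesion, or cognitive decline 4 to 6 weeks after surgery" as a proportion. The Objectives and the sample size text name the same composite. None of them defines the cognitive component or refers to either rule. Experimental Problems says that missed 4-to-6-week visits "could confound analysis of the secondary cognitive end points of the trial".

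**The concern.** Both rules turn the same construct, at the same visit, into a yes/no label, and that label enters the primary endpoint. They are different kinds of rule. One reacts to large falls on a few tests, the other to a modest average fall across the battery. The surrounding text points both ways. The per-test rule is introduced as part of the endpoint. The composite Z rule sits under the analysis plan heading but never mentions the composite. Experimental Problems treats the cognitive end points as secondary.

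Neither rule is complete. The per-test rule does not say whose SD is used or what counts as a test. The composite Z rule standardises to all patients' baseline, while Study Statistics standardises to the control data.

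The event count and the relative risk for the primary comparison depend on the choice. A reader of the results could not tell which analysis had been planned.

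**Working it through.** **1. The plan's own figure.** The sample size text gives 122 per arm for 45% versus 27%, two-sided 5%, 80% power. With mean proportion 0.36 and difference 0.18:

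n = [1.96·√(2·0.36·0.64) + 0.842·√(0.45·0.55 + 0.27·0.73)]² / 0.18² = 110.4.

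The continuity correction gives (110.4/4)·[1 + √(1 + 4/(110.4·0.18))]² = 121.3, so 122. The figure reproduces and is not in dispute.

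**2. Two constructed patients, 10 scores.** The SD of the average of 10 standardised scores with inter-test correlation ρ is √((1 + 9ρ)/10): 0.608 at ρ = 0.3 and 0.742 at ρ = 0.5 (both ρ assumed).
- Every score falls by 0.3 SD. Per-test rule: no decline. Composite fall: 0.3/0.608 = 0.49 or 0.3/0.742 = 0.40, so decline.
- Two scores fall by 1 SD and eight rise by 0.25 SD. Per-test rule: decline. Composite change: (−2 + 2)/10 = 0, so no decline.

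**3. How often the rules disagree.** 200,000 simulated patients per setting. Assumptions not in the documents: no true change, single-test retest correlation r of 0.7 or 0.8, inter-test correlation ρ of 0.2 or 0.5, independent errors, baseline SD as reference. Nine scores are used, being those Appendix B spells out: Rey Auditory 3, word association 1, Trail Making 2, Pegboard 2, Symbol Digit 1.

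| r, ρ | Per-test % | Composite Z % | Per-test only % | Composite Z only % | Disagree % |
|---|---|---|---|---|---|
| 0.7, 0.2 | 23.8 | 26.6 | 9.1 | 11.9 | 21.0 |
| 0.7, 0.5 | 24.0 | 19.5 | 11.9 | 7.4 | 19.3 |
| 0.8, 0.2 | 9.4 | 22.3 | 3.0 | 15.9 | 18.9 |
| 0.8, 0.5 | 9.4 | 14.4 | 4.3 | 9.3 | 13.6 |

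Analytic check of the composite Z column: the composite retest correlation is R = 1 − (1 − r)/(1 + 8ρ), and the share labelled as decline is Φ(−0.3/√(2(1 − R))). R = 0.885, 0.94, 0.923 and 0.96 give 26.6, 19.3, 22.2 and 14.4%, in agreement with the table.

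**4. Effect on the primary composite.** The rule matters only in patients without a DWI lesion. Detection of Brain Injury cites 26 to 50% from other series and adds "we found DWI lesions after surgery in 56% of patients". Taking 26% and 56%, assuming independence and leaving stroke aside, each figure is multiplied by 0.74 or 0.44.

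| r, ρ | Status changes %, DWI 26% / 56% | Event rate, composite Z minus per-test (points) |
|---|---|---|
| 0.7, 0.2 | 15.6 / 9.3 | +2.0 / +1.2 |
| 0.7, 0.5 | 14.3 / 8.5 | −3.3 / −2.0 |
| 0.8, 0.2 | 14.0 / 8.3 | +9.5 / +5.7 |
| 0.8, 0.5 | 10.1 / 6.0 | +3.7 / +2.2 |

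Of 244 patients, 6.0 to 15.6% is about 15 to 38.

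Appendix B can be read as 7 tests (Trail Making A and B counted separately) or as 10 scores (if the Rey Complex Figure gives one). Over 7 to 10 scores, composite disagreement is 6.0 to 16.4%, and the event-rate difference runs from −7.1 to +13.4 points.

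**5. Using the plan's own correlation.** The cognitive sample size assumes a within-patient correlation of 0.7, which may include real change. Error correlation between tests was set so that R = 0.70, with 9 scores and the same four settings. The composite Z rule then labels Φ(−0.3/√0.6) = 34.9% in each, and the per-test rule labels 23.6, 21.2, 12.0 and 10.0%. They disagree in 17.6, 15.1, 23.2 and 24.9%, of which per-test only is 3.2, 0.6, 0.2 and 0.0%. At composite level, disagreement runs from 15.1 × 0.44 = 6.6% to 24.9 × 0.74 = 18.4%. The composite Z rule gives from (34.9 − 23.6) × 0.44 = 5.0 to (34.9 − 10.0) × 0.74 = 18.4 points more events.

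**6. Link to power.** The 45% control rate is attributed to 176 preliminary patients. The outcome reported for them (COx and Neurologic Complications) is DWI lesion, stroke, TIA or clinical delirium, with no cognitive component, so it cannot show which rule was meant. With 122 per arm and a 40% relative reduction, continuity-corrected power is 63% at an assumed control rate of 35%, 80% at 45% and 92% at 55%.

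**The case against.** The text can be read as leaning towards the composite Z rule. It sits under the analysis plan heading. Its own sentences name the visit, the reference SD and what to do with missing tests. An averaged Z score also appears in Study Statistics and underlies the cognitive sample size. That is a fair inference but not a statement of precedence. Study Statistics gives no 0.3 cut-off, and its Z-score text adjoins Aim 1b, the 1-year question.

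The sizes in steps 3 and 4 rest on assumed correlations and imply a composite retest correlation of 0.885 to 0.96, well above the plan's 0.7. This stands. At 0.7 the disagreement is almost wholly one-directional, so the finding that each rule catches patients the other misses depends on the assumptions. The disagreement itself is no smaller.

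The simulation has no treatment arms, so it yields no relative risk or type I error. Under the null, either rule fixed in advance misclassifies both arms alike. The plan also says "Individuals making the neurologic assessments and performing data analysis will be blinded to the intraoperative management group", which limits the scope for choosing a rule after seeing results by arm. Both points are correct, but neither tells a reader which result was planned.

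The direction of the 0.3 cut-off is clear enough in context, since timed tests are reversed so that higher is better. The origin of the 45% is a related but separate matter. The conclusion depends on neither.

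**Conclusion.** The concern holds. The plan contains two incompatible binary definitions of a primary endpoint component and no order of precedence. That conclusion rests on the text alone and carries high confidence.

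The size is illustrative. Under no true change and the stated correlations, roughly 6 to 16% of patients would change primary status (7 to 18% with the composite correlation at 0.7). The event rate could move by several points, with the direction depending on the correlations and on how many scores count. These are not estimates from trial data. The point must be fixed before the primary analysis.

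**What to change.** Before unblinding, amend the Neurocognitive Function paragraph and the Statistical Analysis Plan section so that both name the same one of the two existing rules for the primary composite. State it as a fall in score, give the reference SD, and list which Appendix B scores count. If the composite Z rule is chosen, reconcile its reference population with the one in Study Statistics. Report the other rule as a pre-specified sensitivity analysis, and align the word *secondary* in Experimental Problems with the choice.

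Also state whether the 45% control rate corresponds to the chosen definition. If it does not, restate the expected rate and the power.

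The cost is a text change and one extra analysis, with no new data. The restated rate or power may be less favourable than the present one.

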### **Magnetic Resonance Imaging**

Brain ischemic lesions detected with diffusion-weighted imaging are a component of the primary outcome of this study. Brain MRI will be performed between postoperative days 3 and 14. The imaging sequences will include oblique axial diffusion-weighted images from which apparent diffusion coefficient (ADC) maps will be calculated, perfusion-weighted images, T2, FLAIR, and 3D spoiled gradient-echo (SPGR; which allows 3dimensional reconstruction, comparable to MPRAGE) scans. These data will be acquired on an instrument TBD. Diffusion-weighted trace images are obtained using a

multi-slice, isotropic, single-shot EPI sequence, with  $b_{max} = 1000$  s/mm^2 and TR/TE = 10,000/120 msec. Corresponding ADC maps will be used to identify infarcted tissue. For perfusion-weighted imaging, single-shot gradient echo EPI perfusion images (TR/TE = 2000/60 msec) are obtained with a 20 mL Gd-DTPA (Gadolinium) bolus power injected at 5 mL/sec at the start of the scan. These scans are used to generate maps of the time-to-peak arrival of contrast across voxels in the region of interest, relative to the homologous region of interest in the unaffected hemisphere. Given concerns about the potential for nephrogenic systemic fibrosis from gadolinium contrast in subjects with renal failure, the creatinine level of all patients will be measured before the MRI. Gadolinium will not be given to individuals with an estimated glomerular filtration rate  $\leq 60$  mL/min or to those who need dialysis after surgery (by FDA). In such patients, only diffusion-weighted imaging without gadolinium administration will be performed as needed for determining the primary outcome. The FDA Web site states that “there are no reports received of individuals with normal or even moderately impaired renal function developing NSF [http://www.fda.gov/cder/drug/infopage/gcca/qa\\_200705.htm](http://www.fda.gov/cder/drug/infopage/gcca/qa_200705.htm).

In previous work by members of the investigative team, inter-observer point-to-point agreement for analysis of the time-to-peak delay in each area for 12 scans was 83% for calculating the delay to the nearest 0.1 sec and 100% for calculating the delay within 0.2 sec. We will register each image (first registering the corresponding SPGR scans) to a spatial standard, a digital form of the Montreal Neurological Institute atlas, using local registration methods or image warping, in which each voxel is individually displaced. This technique results in better registration to an atlas than do global methods. Registered images are first read by a neuroradiologist and reported in the patient's medical record as part of standard Department of Radiology policy at Northwestern Memorial Hospital. Any subject who enrolls in this study with a history of retained metal in their head and/or eye(s) will have an x-ray of the head done in order to determine if it will be safe to proceed with the MRI. If it is deemed safe for the subject the MRI will be obtained.

Additionally, stored images will be independently analyzed by one of two investigators (TBD) blinded to patient outcomes. The images will be assessed for nonischemic pathology, the presence and location of prior cerebrovascular disease, new acute ischemic lesions, global cerebral edema, and hemorrhages. Acute ischemic lesions will be depicted as a hyperintense signal on the diffusion-weighted images and hypointense signal on the ADC map. ADC can be calculated on a pixel-by-pixel basis. Based on the location, size, and pattern of distribution, the ischemic infarct will be classified into one of four categories: small subcortical infarction (lesion that is  $< 1$  cm in diameter located in the basal ganglia, thalamus, or brainstem); territorial infarction (lesion located in a vascular distribution, usually resulting from large vessel occlusion); watershed infarction (lesion located in the border zone between vascular territories); or multiple emboli (multiple lesions in one or several different vascular territories). The number of acute lesions detected by diffusion-weighted imaging will be counted, and the total infarct volume will be traced and measured volumetrically by a technician using the Image J software. The sum of infarcts and infarct volume will be recorded in addition to the categorization

of the infarcts as described above. *The primary MRI outcome will be a comparison of the number of diffusion-weighted imaging lesions for patients in the blood pressure Intervention Group with that of the Control Group.*

Secondary analysis will include total infarct volume, location in cortical or subcortical regions, and the ratio of diffusion-weighted imaging lesion size to perfusion-weighted imaging defect size.

MRA will be obtained by contrast-enhanced MRA (CE MRA), using IV contrast at the time of brain MRI. In the event that gadolinium is not administered, MRA of the neck will be carried out with 2D time of flight (TOF) imaging. When gadolinium is administered, neck MRA will be 3D TOF of the neck. MRA of the head will be 3D TOF regardless of use of gadolinium. Measurements of arterial stenosis on MRA will vary depending on the location of the vessel; standard measurements are made by a neuroradiologist, and these will be replicated by one of the investigators (TBD). For extracranial carotid stenosis, the technique is that used in the North American Symptomatic Carotid Endarterectomy Trial (NASCET) (Fig 7).

[figure not shown]
Intracranial arterial stenosis of the most clinically important major vessels (middle cerebral artery, basilar artery, intracranial internal carotid artery) and the extracranial vertebral arteries, will be measured based on the methods used in the Warfarin- Aspirin Symptomatic Intracranial Disease study.

The percent stenosis of a major intracranial artery will be defined as  $[(1 - (\text{Dstenosis}/\text{Dnormal})) \times 100]$ , where

stenosis = the diameter of the artery at the site of the most severe degree of stenosis and normal= the diameter of the proximal normal artery.

For the middle cerebral, intracranial vertebral, and basilar arteries, normal will be defined as the diameter of the widest part of a normal segment of the proximal part of the artery. If this portion of the artery is not normal, then normal will be defined as the diameter of widest part of the distal portion of the artery. When the entire intracranial artery has atherosclerotic narrowing, the most distal part of the normal segment of the artery supplying the vessel will be used for determining normal.

Brain imaging might result in the detection of an unexpected condition, such as a brain mass, aneurysm, or vascular malformation. In the event of such findings, the patient, and his/her family and clinical physicians will be notified, and the patient will be referred for clinical management.

**Fig 7.** Position of measurements to be recorded from neck MRA for degree of internal carotid artery stenosis.  $[(1 - (a/c)) \times 100]$  gives the result as calculated in the NASCET trial. Adapted from Young et al., 1996.

